10.3 Best Response

This is calculated from the sequence of objective statuses.

- a. CR: Two or more objective statuses of CR a minimum of four weeks apart documented before progression or symptomatic deterioration.

- b. PR: Two or more objective statuses of PR or better a minimum of four weeks apart documented before progression or symptomatic deterioration, but not qualifying as CR.
- c. Unconfirmed CR: One objective status of CR documented before progression or symptomatic deterioration but not qualifying as CR or PR.
- d. Unconfirmed PR: One objective status of PR documented before progression or symptomatic deterioration but not qualifying as CR, PR or unconfirmed CR.
- e. Stable/no response: At least one objective status of stable/no response documented at least 6 weeks after registration and before progression or symptomatic deterioration, but not qualifying as anything else above.
- f. Increasing disease: Objective status of progression within 12 weeks of registration, not qualifying as anything else above.
- g. Symptomatic deterioration: Objective status of symptomatic deterioration within 12 weeks of registration, not qualifying as anything else above.
- h. Inadequate assessment, response unknown: Progression or symptomatic deterioration greater than 12 weeks after registration and no other response category applies.

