1.2 Secondary Objectives

- a. To evaluate the overall response rate (confirmed and unconfirmed, complete and partial responses) in the subset of patients with measurable disease treated with afatinib plus cetuximab compared to afatinib alone.
- b. To assess the safety of each treatment arm when used in the first-line setting.
- c. To compare time to treatment failure and time to treatment discontinuation (as defined in [Sections 10.5](#) and [10.6](#)) between randomized to afatinib in combination with cetuximab versus afatinib alone.
- d. To compare overall survival (OS) between the arms.

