Preclinical work in mouse models of *EGFR* mutant lung cancer harboring the *EGFR* T790M mutation has shown that the combination of afatinib and cetuximab results in tumor regression, while neither drug alone was effective. (17) These observations led to a Phase Ib/II clinical trial of this drug combination in which patients with *EGFR* mutant lung cancer that was resistant to erlotinib or gefitinib received afatinib 40 mg po daily along with cetuximab at escalating doses starting at 250 mg/m² and increasing up to a predefined maximum dose of 500 mg/m². (18) The dose escalation portion of this trial demonstrated no dose limiting toxicities; therefore the recommended Phase II dose of cetuximab was 500 mg/m² IV q 2 weeks when given in combination with afatinib 40 mg po daily. Results of the first 96 evaluable patients treated in the expansion cohort showed an objective response rate of 30%, with 75% of patients showing partial response or stable disease (Figure 2). (19) The median PFS was 4.7 months. Importantly,

responses occurred in patients with confirmed T790M mutation in their cancers as well as in those that did not have a T790M mutation, which was an unexpected finding given the results of the preclinical studies. Although several other treatment strategies have been pursued in this patient population including erlotinib plus cetuximab and afatinib alone, none have shown the benefit that was seen with the combination of afatinib plus cetuximab. (20,21,22,23) Given the promising results in the resistant setting, we hypothesize that patients may derive an even greater benefit if the combination is used in the upfront, treatment-naïve setting with the goal of delaying the development of resistance.

In the Phase Ib/II trial of afatinib and cetuximab, adverse events resulted in trial discontinuation in 19% of patients (Table 1). It is unknown whether the toxicity will be similar when this treatment is used in the first-line setting.

Table 1. Toxicity in the Phase Ib/II Trial of Afatinib/Cetuximab

Patients with adverse event (n=100)	Grade 1-2	Grade ≥ 3	All grades
Rash/acne, n	79	18	97
Diarrhea, n	64	7	71
Fatigue, n	52	9	61
Nausea, n	50	3	53
Xerosis, n	49	3	52
Stomatitis, n	50	1	51
Nail effect, n	48	0	48

Inclusion of Women and Minorities

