7.6 Criteria for Removal from Protocol Treatment

- a. Unequivocal progression of disease or symptomatic deterioration (as defined in [Section 10.2e](#)). Patients may continue to receive study treatment after radiographic progression per RECIST 1.1 as long as they continue to experience clinical benefit in the opinion of the treating physician. Patients who continue to receive study treatment after progression will continue with the on study requirements (as indicated by the study calendar "Cycle X" columns), **not** the off study requirements (as indicated by the study calendar column titled "F/U After Prog").
- b. Unacceptable toxicity.
- c. Women who become pregnant while participating in the study must discontinue study medication immediately. The pregnancy must be reported following procedures detailed in [Section 16.1](#).
- d. Treatment delay for any reason > 28 days from planned date of treatment.
- e. The patients may withdraw from the study at any time for any reason.

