- β Physical exam to include cardiopulmonary examination, examination of abdomen and regional lymph nodes, and assessment of mental and neurological status.
- Ω After off treatment prior to disease progression, scans for disease assessment and physical assessments (with lab tests performed at the discretion of the treating investigator) should take place every 8 weeks until progression.
- % After off treatment following disease progression, physical assessments (with lab tests performed at the discretion of the treating investigator) should take place every 6 months for three years from the time of registration.
- ¥ If institution is participating in repeat biopsy substudy. See [Section 15.5](#) and [15.6](#).
- ◊ Only if patient has brain metastases at baseline.
- § Only if clinically indicated.
- ¶ Diphenhydramine must be given prior to first dose of cetuximab and is recommended prior to subsequent doses (see [Section 7.1](#)).
- ? Vital signs should be checked prior to each cetuximab administration, midway through the infusion, at the completion of the infusion, and one hour post the infusion.
- ã See “Best Practices for SWOG Studies” at the following URL for acceptable time windows for procedures and assessments:
<https://www.swog.org/sites/default/files/docs/2017-10/Best%20Practices%20upddate.pdf>.
- ¿ PET scans are recommended as a complement to other scans (see [Section 10.2d](#)). They are not required.

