14.4 Data Submission Overview and Timepoints

a. WITHIN 7 DAYS OF INITIAL REGISTRATION, SUBMIT:

S1403 Onstudy Form

Baseline Tumor Assessment Form (RECIST 1.1)

Smoking Status Assessment Form

Radiology reports from all scans performed to assess disease at baseline

Pathology report from initial diagnosis

Pathology report from a CLIA-certified lab documenting presence of a sensitizing EGFR mutation

S1403 Local Pathology Review Form (see [Section 18.3](#))

NOTE: Upload radiology reports, pathology reports, and the S1403 Local Pathology Review Form via the Source Documentation: Baseline form in RAVE®.

b. SUBMIT:

Specimens as specified in [Section 15.0](#)

c. WITHIN 14 DAYS AFTER EACH CYCLE OF TREATMENT (1 CYCLE = 28 DAYS), SUBMIT:

S1403 Treatment Form

S1403 Adverse Event Form

d. WITHIN 14 DAYS AFTER EACH DISEASE ASSESSMENT (SEE STUDY CALENDAR FOR SCHEDULE) UNTIL PROGRESSION (AS DEFINED IN SECTION 10.2e), SUBMIT:

Follow-Up Tumor Assessment Form (RECIST 1.1)

Radiology reports from all scans performed to assess disease*. Physician must note tumor measurement in patient records.

*NOTE: Upload reports via the Source Documentation: Follow-up form in RAVE®

e. WITHIN 7 DAYS OF DISCONTINUATION OF PROTOCOL TREATMENT, SUBMIT:

Off Treatment Notice

S1403 Treatment Form

S1403 Adverse Event Form

Smoking Status Assessment Form

f. WITHIN 14 DAYS OF PROGRESSION OR RELAPSE, SUBMIT:

NOTE: IF PATIENT REMAINS ON TREATMENT FOLLOWING PROGRESSION (SEE SECTION 7.6a, CONTINUE TO SUBMIT THE S1403 ADVERSE EVENT FORM AND S1403 TREATMENT FORM AFTER EVERY CYCLE OF TREATMENT AS OUTLINED IN SECTION 14.4c).

Follow-Up Tumor Assessment Form (RECIST 1.1)

Site(s) of Progression/Relapse Form

Radiology reports from all scans performed to assess disease. Physician must note tumor measurement in patient records.

NOTE: Upload reports via the Source Documentation: Follow-up form in RAVE®.

g. ONCE OFF ALL PROTOCOL TREATMENT SUBMIT EVERY 6 MONTHS FOR THE FIRST 2 YEARS AND THEN AT THE END OF YEAR 3:

Advanced NSCLC Follow-Up Form

Late Effects Form (if prior to treatment for progression or relapse or a second primary, and prior to non-protocol treatment, the patient experiences any severe [Grade ≥ 3] long term toxicity that has not been previously reported).

h. WITHIN 4 WEEKS OF KNOWLEDGE OF DEATH:

Notice of Death

If patient was still on treatment, submit materials specified in Section 14.4e; otherwise, submit Advanced NSCLC Follow-Up Form.

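### Best response has no cut-off at the start of non-protocol systemic therapy, so a response first reached on a later drug is credited to the assigned regimen

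*Combined protocol and SAP*

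**What the plan says.** **Endpoint.** Objective 1.2a is the "overall response rate (confirmed and unconfirmed, complete and partial responses) in the subset of patients with measurable disease". A single CR or PR status is therefore enough.

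**Window.** Of best response, Section 10.3 says: "This is calculated from the sequence of objective statuses". Categories a to d, which cover confirmed and unconfirmed CR and PR, stop only at progression or symptomatic deterioration. The unconfirmed PR category is typical: "Unconfirmed PR: One objective status of PR documented before progression or symptomatic deterioration but not qualifying as CR, PR or unconfirmed CR". Sections 1.2, 10.2, 10.3 and 11 set no limit at the end of protocol treatment or at the start of another anticancer therapy.

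**Scans that feed the sequence.** Section 7.6b lists "Unacceptable toxicity" as a reason to leave protocol treatment. The footnotes to both calendars (9.1 and 9.2) cover patients who have stopped without progressing: "After off treatment prior to disease progression, scans for disease assessment and physical assessments" continue every 8 weeks until progression. Under Section 14.4d, tumor assessment forms are due "WITHIN 14 DAYS AFTER EACH DISEASE ASSESSMENT (SEE STUDY CALENDAR FOR SCHEDULE) UNTIL PROGRESSION".

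**Where response is used.** It is compared between arms in Sections 11.2c and 11.2d. Section 18.1 uses it as the measure of sensitivity for T790M (part a) and gene amplification (part b), and as an outcome for EGFR H-score (part d).

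**The concern.** The response comparison is meant to describe the activity of the assigned regimen. Objective 1.2a frames it as response "in the subset of patients with measurable disease treated with afatinib plus cetuximab compared to afatinib alone". A patient who stops without progressing, starts another active drug and shows a PR at the next scan has responded to that drug, yet 10.3 counts the response for the randomized arm.

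Two things are at stake:

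- **Misclassification of individual responders.** This can happen in either arm, and it affects the biomarker analyses even if the arms switch equally often.
- **A possible shift in the difference between arms.** This arises only if one arm has more early switching without progression.

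The gap looks like an omission. Section 7.4b already bars irradiated areas from response assessment, but there is no parallel rule for systemic therapy. Section 14.4g uses non-protocol treatment as a cut-off for the Late Effects Form. Section 11.2c gives newly approved later-line regimens as one reason for moving the primary endpoint from OS to PFS, so later therapy was seen as material.

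**Working it through.** **1. The plan's own figure.** Section 11.2c gives 90 patients per arm, a 1-sided 5% chi-squared test, a 22-point difference and 93% power. The evaluable number is 212 × 0.85 = 180. Section 11 states no control response rate, so I assume 56%, the LUX-Lung 3 afatinib rate in Section 2.0. With pooled variance under the null:

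- Null SE = √(0.67 × 0.33 × 2/90) = 0.0701
- Alternative SE = √((0.56 × 0.44 + 0.78 × 0.22)/90) = 0.0682
- Power = Φ((0.22 − 1.645 × 0.0701)/0.0682) = 93.8%

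This agrees with the stated 93%. Power is not in dispute; the step only sets the scale.

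**2. Route to a credited response.** The patient stops without progression (7.6), is scanned every 8 weeks (9.1, 9.2), has forms submitted until progression (14.4d), and the status enters the sequence (10.3). One unconfirmed PR is enough (1.2a). No step asks what drug the patient was taking.

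**3. Size, first illustration.** Overstatement in an arm = (proportion switching before any response) × (response rate on the next drug). The documents give no switch rates. Assume 5-10% in Arm 1, 2% in Arm 2, and 56% response after switching.

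| | Arm 1 | Arm 2 | Net |
|---|---|---|---|
| 5% v 2% | 0.05 × 0.56 = 2.8 points | 0.02 × 0.56 = 1.1 points | 1.7 points |
| 10% v 2% | 0.10 × 0.56 = 5.6 points | 1.1 points | 4.5 points |
| Equal rates | same | same | 0 |

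The net figure is about 1.5 to 4 patients of 90 (0.017 × 90 and 0.045 × 90). If the true rate is 56% in both arms, the nominal 5% test would reject in about 8% to 15% of trials.

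**4. Size, second illustration.** Section 2.0 reports that in the Phase Ib/II trial "adverse events resulted in trial discontinuation in 19% of patients". Suppose 19% of Arm 1 stop, 25-60% of them have not yet responded, and 30-56% of those respond to the next drug. The addition to Arm 1 runs from 0.19 × 0.25 × 0.30 = 1.4 points to 0.19 × 0.60 × 0.56 = 6.4 points, or 1.3 to 5.7 patients of 90. The false-positive rate then depends on stopping in Arm 2:

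| Arm 2 stopping for adverse events | False-positive rate (nominal 5%) |
|---|---|
| 0% | 7-22% |
| 5% | 7-16% |
| 10% | 6-11% |
| 19% | 5% |

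**The case against.** **The text is silent rather than permissive.** Section 10.3 does not mention later therapy, and the reference in objective 1.2a to patients treated with each regimen points to the narrower reading. That is fair as to intent. But the operative rule is 10.3, and applied as written it counts these responses.

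**A reader might infer that the rule favors the combination.** The documents do not establish this:

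- The 19% comes from a TKI-resistant population given one regimen, and Section 2.0 says it is unknown whether first-line toxicity will be similar.
- Under Section 8.3, Arm 1 patients can stop cetuximab for hypersensitivity, hypomagnesemia or at dose level -3 and stay on protocol afatinib. Their responses belong to Arm 1 by design.
- The top of the false-positive range requires that nobody in Arm 2 stops for an adverse event.

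**A reader might picture a patient who stops for rash in week 3 and has switched by week 5.** That is possible through removal for toxicity or withdrawal (7.6), but it is not the ordinary path. Section 8.3g describes a hold, resumption at a reduced level, and discontinuation if rash has not resolved within 28 days.

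**A reader might also infer that intolerance is hidden.** It is not. Early discontinuation is an event in time to treatment failure (10.5), any discontinuation is an event in time to treatment discontinuation (10.6), and toxicity is compared between arms.

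**The illustration leans high.** It gives every switcher the full 56% response rate and credits none of those responses to the weeks on assigned treatment.

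These points remove the directional claim and limit the size. The gap in the definition stands.

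**Conclusion.** The definition needs correcting. Sections 10.3, 9.1, 9.2 and 14.4d together credit the assigned regimen with a response first reached on non-protocol systemic therapy. This follows from the text without any numerical assumption, and it affects objective 1.2a and the response analyses in Section 18.1.

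Bias between arms is conditional. It needs unequal early switching without progression, which is plausible because Arm 1 adds a second EGFR agent, but is not shown. The net 1.7-4.5 points rests on assumed switch rates and an assumed 56% response after switching. It is small beside the 22-point design difference and vanishes if the arms switch equally. Response is a secondary endpoint, and the primary PFS analysis is not affected.

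**What to change.** - In 10.3 a-d, count a status only if it precedes the earliest of progression, symptomatic deterioration and the start of non-protocol systemic anticancer therapy.
- Keep measurable patients with no such response in the denominator as non-responders.
- Report the current rule as a sensitivity analysis.
- Apply the same definition to the response analyses in Section 18.1.
- Confirm that the start date of non-protocol therapy is captured. Section 14.4g refers to such treatment as a condition for one form, but does not show that a date is collected, and form contents are not in the documents.

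**Cost.** One sentence in 10.3 and possibly one data field. Scans, sample size and the PFS definition stay as they are. The response rate may fall slightly. A patient who switches before the first scan, at about week 8, becomes a non-responder even if already responding to assigned treatment. If early switching is more common in one arm, that arm is understated to this extent, so both versions should be shown.

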10.4 Performance Status

Patients will be graded according to the Zubrod Performance Status Scale.

POINT	DESCRIPTION
0	Fully active, able to carry on all pre-disease performance without restriction.
1	Restricted in physically strenuous activity but ambulatory and able to carry out work of a light or sedentary nature, e.g., light housework, office work.
2	Ambulatory and capable of self-care but unable to carry out any work activities; up and about more than 50% of waking hours.
3	Capable of limited self-care, confined to bed or chair more than 50% of waking hours.
4	Completely disabled; cannot carry on any self-care; totally confined to bed or chair.

10.5 Time to Treatment Failure

From date of registration to date of first documentation of progression or symptomatic deterioration (as defined above), early discontinuation of treatment, or death due to any cause. Patients last known not to have failed treatment are censored at the date of last contact.

10.6 Time to Treatment Discontinuation

From date of registration to date of discontinuation of treatment or death due to any cause. Patients last known not to have discontinued treatment are censored at the date of last contact.

10.7 Time to Death

From date of registration to date of death due to any cause. Patients last known to be alive are censored at date of last contact.

10.8 Progression-Free Survival

From date of registration to date of first documentation of progression or symptomatic deterioration (as defined above), or death due to any cause. Patients last known to be alive without report of progression are censored at date of last disease assessment.

11.0 STATISTICAL CONSIDERATIONS

11.1 Sample Size with Power Justification

The primary objective of the Phase III study is to compare overall survival (OS) in *EGFR* mutation positive, previously untreated, advanced NSCLC patients randomized to afatinib plus cetuximab versus afatinib alone. The primary objective of the Phase II interim analysis is to evaluate if there is sufficient evidence to continue to the Phase III component by comparing progression-free survival (PFS) between patients randomized to afatinib alone versus afatinib in combination with cetuximab in this study.

Randomization will be stratified by performance status (0-1 versus 2) and *EGFR* mutation type (exon 19 deletion versus L858R mutation). It is assumed that among patients with the exon 19 deletion, the median OS with afatinib alone will be 32 months based on the LUX-Lung 3 and 6 studies. It is also assumed that 56% of patients will have the exon 19 deletion. Further, it is assumed that among patients with the L858R mutation, the median OS with afatinib alone will be 21 months also based on the LUX-Lung studies. The median PFS for patients is assumed to be 13.7 months for patients with the exon 19 deletion and 10.8 months among patients with the L858R mutation among patients randomized to afatinib alone based on the LUX-Lung 3 study.

The addition of cetuximab will be judged to be superior if the true increase in median OS is 45% (hazard ratio = 0.69). A design with 90% power (not adjusting for Phase II analysis) and 0.025 1-sided type I error would require 304 deaths. Assuming exponential survival and uniform accrual, with 48 months of accrual and 14 months of follow-up, this design results in a sample size of 576 eligible *EGFR*-mutant NSCLC patients to detect a 45% improvement in median PFS using a 1-sided 0.025 level stratified log-rank test. Under these design parameters, an observed 25% or greater improvement in median OS (equivalent to an increase in median OS of 8 and 5.5 months for exon 19 and L858R patients will be considered evidence of benefit with the addition of cetuximab to afatinib. Assuming a 5% ineligibility rate, the total target accrual is 605.

11.2 Analysis Plan Including Plans for Formal Interim Analysis

a. Phase II Interim Analysis

The Phase II interim analysis will evaluate early stopping for futility alone based on PFS. A design with 90% power to detect a 90% increase in median PFS (from

13.7 to 26 months among exon 19 deletion patients and from 10.8 to 20.5 among L858R mutation patients) and 10% type I error would require 64 progression events. The Phase II interim analysis will take place upon the observation of 64 PFS events, approximately 17 months after study activation when it is expected that 212 patients have been accrued. Conditions for recommending stopping the study early for lack of efficacy will be if the alternative hypothesis is rejected at the 10% level using a 1-sided modified log-rank test. Under these design parameters, an observed 38% or greater improvement in median PFS (equivalent to an increase in median PFS of 5.2 and 4.1 months respectively for exon 19 and L858R strata) will be considered evidence of benefit with the addition of cetuximab to afatinib. In addition to the PFS assessment, toxicity rates will be evaluated and compared between the two arms at this analysis. An additional objective of the Phase II interim analysis will be to evaluate the safety of cetuximab in combination with afatinib. Toxicities of specific focus will be grade ≥ 3 rash and diarrhea.

b. Phase III Interim Analyses

A second interim analysis evaluating early signs of efficacy or futility will take place when 152 (50% of expected) deaths have been observed, approximately 40 months after study activation, when approximately 80% of patients have been accrued to the study. This analysis will evaluate stopping early for efficacy testing the null hypothesis using a 1-sided 0.0025 level log-rank test and stopping early for futility testing the alternative hypothesis at the 0.01 level using a modification of the test allowing for relative risks not equal to one (the approximate HR threshold for futility is 1.00). Should the study not cross any boundaries, the study will continue accrual to the second and final interim analysis.

A final interim analysis will take place when 75% of the expected deaths (228) have been observed, which is expected to take place around completion of accrual at 50 months after activation. The same rules for early stopping for either futility or efficacy will be implemented at this analysis. Should no boundaries be crossed, the recommendation will be to continue to full follow-up.

The final analysis will take place upon the observation of 304 deaths (expected around 14 months after completion of accrual) or at maximum of 2 years after the last patient was accrued, whichever comes first. This analysis will be performed using a 1-sided log-rank test, with significance level of 0.024 to account for the interim analyses.

					Approximate HR Boundary	
Analysis	Information	Events	Anticipated accrual n (%)	Study time	Futility	Efficacy
Phase II interim	14% PFS events*	64 PFS	212 (37%)	17 months	1.38	N/A
Phase III interim #1	50% OS events	152 OS	461 (80%)	40 months	1.006	1.56
Phase III interim #2	75% OS events	228 OS	576 (100%)	50 months	1.07	1.44
Final Analysis	100% OS events	304 OS	576 (100%)	62 months	1.25	1.25

* The expected number of PFS events by the end of the Phase III is 446.

c. **REVISED STATISTICAL DESIGN**

Due to the approval of post-first-line regimens and a lower than anticipated accrual rate, the design of the study has been modified. First, the primary endpoint has been changed from OS to PFS to reflect PFS as a relevant endpoint, which also results in a reduction in sample size. In addition, a hard-stop on accrual at a specific time point, even if the accrual target is not met, has been imposed. The following sections lay out the specific details for this new design.

The original design specifies that the Phase II interim analysis to evaluate for stopping for futility will be performed when 64 progression events have been observed, at which time it is expected that 212 eligible patients will have been accrued. In the new design, the sample size for this study has been reduced to the anticipated Phase II sample size of 212 patients with a hard stop in accrual on October 1, 2018, if the accrual to the study has not reached 212 patients.

The primary objective for the new design is to compare PFS between the arms at the 1-sided 0.025 level. This analysis would take place when 134 PFS events or 70% of the events among eligible patients have been observed (whichever comes first and will depend on sample size attained). With 134 PFS events, this study has 90% power to detect a hazard ratio of 0.57 (75% improvement). The following table describes the analysis as a function of how many patients are accrued by the time of study closure:

Final Sample Size	# events at analysis	HR with 90% power	improvement in PFS
160	112	0.54	85%
180	126	0.56	78%
200	134	0.57	75%
212	134	0.57	75%

An interim analysis will take place when 64 PFS events have been observed. This analysis will be presented to the SWOG Data and Safety Monitoring Committee at the SWOG Group Meeting closest to this number of events. This analysis will evaluate if there is evidence to recommend early stopping of the study for futility by testing the null hypothesis at the 0.5 level, using a stratified log-rank test. If the p-value is 0.5 or greater, than the recommendation will be that there is insufficient evidence to continue accrual to this study.

Secondary Objectives under the revised design are to compare response rates, OS, time to treatment failure (TTF), time to treatment discontinuation (TTD), and toxicity.

Assuming 212 patients enrolled over 36 months with 14 months of additional follow-up, a one-sided log-rank test with an alpha of 0.025 has 90% power to detect an OS hazard ratio of 0.5, corresponding to a 2-fold increase in median OS, under the exponential distribution. Similarly, if it is assumed that the median TTF is 11 months, and the median TTD is also 11 months, there will be 92% power to detect a 70% increase in medians (hazard ratio of 0.59) for each of these endpoints.

Assuming 85% of patients will have measurable disease, 180 patients will be evaluable for the response comparison between arms. Response rates between the arms will be compared using a chi-squared test of independence at the 1-sided 5% level. With 90 patients per arm, this design has 93% power to detect at least a 22% difference in response rates between the arms and within each arm the rates can be estimated to within 10% with 95% confidence.

Toxicity rates between arms will be assessed using a chi-squared or Fisher's exact test (as appropriate) at the 1-sided 5% level. Assuming all eligible patients are evaluable for toxicities, rates can be estimated to within 10% with 95% confidence and any toxicity with at least 5% prevalence has almost a 100% chance of being observed. With 106 patients per arm, this design has 92% power to detect at least a 20% difference between the arms.

d. Secondary Objectives

Additional analyses will be to compare response rates, OS, time to treatment failure (TTF), time to treatment discontinuation (TTD), and toxicity.

Assuming 212 patients enrolled over 36 months with 14 months of additional follow-up, a one-sided log-rank test with an alpha of 0.025 has 90% power to detect a OS hazard ratio of 0.5, corresponding to a 2-fold increase in median OS, under the exponential distribution. Similarly, if it is assumed that the median TTF is 11 months, and the median TTD is also 11 months, there will be 92% power to detect a 70% increase in medians (hazard ratio of 0.59) for each of these endpoints.

Assuming 85% of patients will have measurable disease, 180 patients will be evaluable for the response comparison between arms. Response rates between the arms will be compared using a chi-squared test of independence at the 1-sided 5% level. With 90 patients per arm, this design has 93% power to detect at least a 22% difference in response rates between the arms and within each arm the rates can be estimated to within 10% with 95% confidence.

Toxicity rates between arms will be assessed using a chi-squared or Fisher's exact test (as appropriate) at the 1-sided 5% level. Assuming all eligible patients are evaluable for toxicities, rates can be estimated to within 10% with 95% confidence and any toxicity with at least 5% prevalence has almost a 100% chance of being observed. With 106 patients per arm, this design has 92% power to detect at least a 20% difference between the arms.

